10.2 Resistance thermometer (RT)

Contact sensor (~15 mm²) affixed between 3rd–4th metacarpals, mid-distance between wrist and MCP joints, secured with medical tape. 1-min sampling from acclimatisation start to end of rewarming. Two-point check vs reference thermometer before each session.

10.3 Quantitative sensory testing (QST)

MDT: Semmes–Weinstein monofilaments (1.65–6.65; 0.008–300 g), vertical application until bending, ~1 s contact; up-down method, threshold from central tendency.

VDT: Rydel–Seiffer tuning fork (64 Hz; 0–8/8 scale), three trials over a bony landmark; mean of three readings.

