1.4 Roles and responsibilities

Sponsor/Institution: Poznań University of Physical Education (Department of Physical Therapy and Sports Recovery).

Scientific lead: [[name]], PhD. Data management/statistics: [[name]], MSc. Thermal imaging lead: [[name]], MSc.

Corresponding author: [[name]], [[contact]].

2. Background and Rationale

Local cryotherapy with ice packs is widely used to alleviate pain and modulate cutaneous temperature and sensation. However, the short-term time-course of rewarming and contemporaneous changes in subjective thermal perception and somatosensory thresholds are not fully characterised in controlled, randomized settings. This study compares a 15-minute hand ice-pack application with a thermoneutral water-pack control, using infrared thermography (IRT) and a resistance thermometer (RT) alongside validated subjective scales and quantitative sensory testing (QST).

3. Objectives

Primary objective:

- To compare the effect of ice-pack vs thermoneutral pack on dorsal hand skin temperature (Tsk) during early rewarming after a 15-minute application.

Secondary objectives:

- To compare immediate post-cooling changes in mechanical detection threshold (MDT) and vibration detection threshold (VDT).
- To compare trajectories and peaks of subjective thermal sensation (TSS), thermal comfort (CS), and pain (VAS) during cooling and immediately post-cooling.
- To characterise agreement and systematic offset between ROI-averaged IRT and single-site RT across matched time points.

4. Trial Design

Randomized, parallel-group, two-arm laboratory experiment with a 1:1 allocation ratio (ice vs thermoneutral water). Single-centre. No blinding of participants; thermal image analysis performed offline by a rater not involved in data collection.

5. Study Setting

Single air-conditioned laboratory (Department of Physical Therapy and Sports Recovery, Poznań University of Physical Education). Ambient conditions monitored throughout (target $\sim 22.5 \pm 1.0$ °C, $55 \pm 7\%$ RH).

6. Participants

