8.2 Key secondary endpoints

- Dorsal hand Tsk at matched time points (I, IV–X) by IRT and RT; between-group differences and IRT–RT offsets.
- MDT change (post-cooling minus baseline; IV–I).
- VDT change (IV–I).
- Subjective scales: TSS (−4 very cold ... +4 very hot), CS (1 comfortable ... 5 extremely uncomfortable), VAS pain (0–100 mm). Outcomes include peak during cooling (II/III) and immediate post-cooling (IV).

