12.3. Blinding

Participants and interventionists were not blinded. Thermal image analysis was performed offline by an assessor not involved in data collection. Raw-data preprocessing/curation ([name]) and statistical analyses ([name]) were conducted by team members who did not take part in the experimental procedures and were blinded to group allocation.

13. Statistical Analysis Plan (SAP)

- **Descriptives:** values as mean \pm SD; Table 1 additionally reports min–max where shown.
- **Normality:** Shapiro–Wilk test.
- **Between-group comparisons at prespecified time points:** Student’s t test (normal) or Mann–Whitney U test (non-normal).
- **Within-group pre–post comparisons:** paired Student’s t test (normal) or Wilcoxon signed-rank test (non-normal).
- **Repeated measures:** two-way repeated-measures ANOVA for Tsk (group \times stage; and IRT vs RT within groups), with Bonferroni-adjusted post hoc tests. Effect size: partial η^2 for RM-ANOVA.
- **Significance:** $\alpha = 0.05$; tests two-sided.
- **Analysis set / missing data:** all randomised participants analysed; no imputation (no losses).

14. Data Management and Sharing

De-identified individual participant data (IPD) and the de-identified summary datasets underlying all tables and figures are openly available in Zenodo (DOI: 10.5281/zenodo.17255092) under a CC BY 4.0 license, with no access restrictions or data-use agreement required. The Zenodo record also includes Supplementary File S1 (exact questionnaire wording/anchors) and the full Research Protocol and prespecified Statistical Analysis Plan. De-identified IPD comprise participant-level values for prespecified outcomes and baseline characteristics; direct identifiers, dates, free-text fields, and rare categories were removed or aggregated to minimise re-identification risk. The dataset will be preserved for at least 5 years; enquiries may be directed to the corresponding author.

15. Ethics

Approved by the Bioethics Committee of the Poznań University of Medical Sciences (Resolution No. 360/11). Conducted in accordance with the Declaration of Helsinki. Minimal risk expected.

16. Monitoring and Harms

Adverse events (e.g., excessive pain, skin irritation) monitored throughout; any event recorded with timing, severity, relatedness, and action taken. No interim analyses; trial duration per session ~60–75 minutes.

17. Amendments and Deviations

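### MDT change is analysed as an unadjusted difference on an unstated scale; ANCOVA of log10 force would fix the scale and recover power

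*Combined protocol and SAP*

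**What the plan says.** Section 3 lists this secondary objective: "To compare immediate post-cooling changes in mechanical detection threshold (MDT) and vibration detection threshold (VDT". Section 8.2 turns it into the endpoint "MDT change (post-cooling minus baseline; IV–I", with no unit and no transformation.

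Section 10.3 gives the instrument as "Semmes–Weinstein monofilaments (1.65–6.65; 0.008–300 g". The first range is the filament index and the second is force. The threshold is obtained by "up-down method, threshold from central tendency". Whether that means an arithmetic mean, a median or a geometric mean is left open, as is the scale on which it is taken.

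Section 13 has no rule specific to MDT. Normality is judged by the "Shapiro–Wilk test". Groups are compared by "Student’s t test (normal) or Mann–Whitney U test (non-normal", and "Within-group pre–post comparisons" use "paired Student’s t test (normal) or Wilcoxon signed-rank test (non-normal". Descriptives are mean ± SD. The only effect size named is partial η², for the repeated-measures ANOVA of skin temperature. No baseline covariate, log step or confidence interval is planned for MDT. I read the between-group test as applied to the change defined in 8.2.

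**The concern.** Index and force lead to different endpoints. A difference in index units is close to a log ratio, whereas a difference in grams depends on where the participant started. The same proportional loss of sensitivity therefore counts far more in someone with a high baseline threshold, and a mean change in grams can rest on a few such people. Averaging the up-down readings raises the same question before any change is computed.

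An unadjusted change score also subtracts the whole baseline value, noise included. With two correlated readings per person, regression on baseline is more efficient. Section 11 puts power at about 0.68 for d = 0.80 with the achieved sample, so an avoidable loss matters. If the rank test is used, the plan leaves only mean ± SD as a summary of effect.

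**Working it through.** **Inputs from the documents.** Group sizes 20 and 19, d = 0.80, two-sided α = 0.05 (Sections 11 and 13); index 1.65–6.65 and force 0.008–300 g (10.3).

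**Assumed inputs.** Log-normal thresholds, SD 0.2–0.6 log10 units, pre–post correlation r = 0.3–0.8, and a cold effect of 0.8 SD of the log10 change. The documents give no MDT variance or correlation.

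**1. The plan's own figures.** The noncentral t calculation gives n = 25.52, so 26 per group, and power 0.682 at 20 versus 19. Both stated figures reproduce. Neither is specific to MDT.

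**2. The two scales.** 300 / 0.008 = 37,500, and log10(37,500) = 4.57 decades. The index spans 6.65 − 1.65 = 5.00 units, or 4.57 / 5.00 = 0.91 decade per unit on average, so it is roughly logarithmic. In grams, doubling from 0.02 to 0.04 g is +0.02 g and doubling from 2 to 4 g is +2 g. Both are +0.30 on log10.

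**3. Cost of the scale alone.** The plan's rule (Shapiro–Wilk, then t or Mann–Whitney) was applied to the same simulated data on both scales, 3,000 trials per setting:

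| SD (log10) | r | Power, gram change | Power, log10 change |
|---|---|---|---|
| 0.3 | 0.3 | 0.70 | 0.69 |
| 0.3 | 0.6 | 0.66 | 0.68 |
| 0.6 | 0.3 | 0.69 | 0.69 |
| 0.6 | 0.6 | 0.63 | 0.69 |

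Over the full assumed range the rule gives 0.58–0.71 in grams and 0.67–0.69 on log10, so the scale costs about 0–10 points. A separate simulation, set up with between-person SD 0.6 and within-person SD 0.15–0.35, found 11–14 points. Those settings imply r = 0.36 / (0.36 + 0.0225) = 0.94 down to 0.36 / (0.36 + 0.1225) = 0.75, and total SDs of √0.3825 = 0.62 to √0.4825 = 0.69. They lie at or beyond the edge of the range used here, and the two results agree.

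**4. Gain from baseline adjustment.** With equal variances, the change has SD σ√[2(1 − r)] and the ANCOVA residual has SD σ√(1 − r²). The ratio multiplies d by √[2 / (1 + r)]:

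- r = 0.3: 0.80 × √(2 / 1.3) = 0.99, power about 0.86
- r = 0.6: 0.80 × √(2 / 1.6) = 0.89, power about 0.78
- r = 0.8: 0.80 × √(2 / 1.8) = 0.84, power about 0.73

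The unadjusted t test on log10 change has 0.68 throughout, by construction. Simulated ANCOVA on log10 force gives 0.71–0.87, in line with these values, and its type I error is about 0.05 (0.04–0.06).

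**5. Adjustment in grams.** ANCOVA on untransformed force gives 0.31–0.79 over the same range. At SD 0.6 and r = 0.3 it gives 0.47, against 0.83 on log10. The log scale is needed to realise the gain.

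**The case against.** A reader might infer that the plan analyses MDT in grams. The documents do not say so. Section 10.3 lists the index beside the force, and if the index is analysed, a plain difference is already close to a log ratio and the scale problem largely disappears. That objection stands. What remains is that the choice is open in a plan that Section 14 calls prespecified, and that the missing baseline adjustment matters on either scale.

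A reader might also quote the power of a t test on gram change, which was as low as 0.24 in one set of assumptions. That is not the plan's analysis. With such skewed data Shapiro–Wilk nearly always sends the comparison to Mann–Whitney, which recovers much of the loss. The fallback is still not a complete answer: ranks of gram changes differ from ranks of log changes, and the rank test supplies no effect estimate.

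Nor does it follow that a gram difference is meaningless. It is well defined, but its size depends on baseline.

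It is also fair to say that change score versus ANCOVA is a general matter for pre–post endpoints, and that the gain should not be credited to the log step alone. At r = 0.3–0.6 most of it comes from adjustment. At r = 0.8 adjustment adds only about 3–5 points (0.71–0.73 against 0.68), and with wide spread the scale then contributes more.

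Finally, the instrument's range says nothing about the spread among healthy male students. At SD 0.2 the scale costs little. MDT is secondary, Section 11 calls the findings exploratory, and the primary endpoint and sample size are untouched.

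**Conclusion.** The point holds in this form: the MDT scale and the averaging rule are unspecified, and the planned comparison is an unadjusted difference where a better analysis of the same values is available. At 20 versus 19 participants, with SD 0.2–0.6 log10 units, r = 0.3–0.8 and an effect of 0.8 SD of the log change, power is about 0.71–0.87 for ANCOVA of log10 force and 0.58–0.71 for the plan's rule in grams. The scale accounts for about 0–10 points of that difference, and baseline adjustment for most of the rest.

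The spread and correlation are assumptions, and discrete filament steps and floor effects are not modelled. There is no sign of an inflated type I error on either scale, so this concerns precision and interpretability rather than validity.

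**What to change.** - **8.2:** define the endpoint on log10 force, comparing MDT at IV between groups with adjustment for MDT at I.
- **10.3:** state that up-down readings are converted to log10 force before averaging, and name the average.
- **13:** compare groups by ANCOVA of log10 MDT at IV on log10 MDT at I. Back-transform the adjusted difference and report the ratio of geometric means with its 95% CI, in place of mean ± SD in grams.

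The existing values suffice and the computing cost is negligible. The change does have a price. Section 11 describes a trial already enrolled, so the change must be dated, justified and labelled post hoc under Section 17. I would keep the plan's own comparison beside it as a sensitivity analysis, stating which scale it uses, and report how many participants sat at the lowest filament, since floor effects and discrete steps could reduce the gain.

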10.4 Subjective scales

TSS (−4...+4; anchors from very cold to very hot), CS (1...5; comfortable to extremely uncomfortable), VAS pain (0–100 mm; no pain to worst pain imaginable). Scripted instructions by the same assessor.

11. Sample Size

An a priori power analysis (G*Power 3.1.9.7) for a two-tailed independent-samples t-test ($\alpha = 0.05$, power = 0.80, anticipated effect size $d = 0.80$) indicated a required sample of 26 participants per group (total $n = 52$). In practice, 39 participants were enrolled and randomised (experimental $n = 20$; control $n = 19$). Of 40 individuals assessed, one was excluded at screening for a health condition. No participants discontinued the intervention or were lost to follow-up. With the achieved sample size, post-hoc power to detect $d = 0.80$ was approximately 0.68; accordingly, findings are interpreted as exploratory/hypothesis-generating.

12. Randomization and Allocation

12.1 Sequence generation

A simple 1:1 computer-generated randomization sequence (no blocking or stratification; superiority framework) was prepared by [name] to map numeric study IDs to groups (ice pack vs thermoneutral control). [name] had no access to personal identifiers.

12.2 Allocation concealment and implementation

At registration, participants received numeric study IDs (ID001–ID039) assigned by [name]. The identity–ID linkage was held by the registrar. Group assignments were concealed until completion of baseline assessments and were disclosed immediately before the intervention. No sequentially numbered opaque sealed envelopes or centralized web-based randomization system were used.

12.3. Blinding

Participants and interventionists were not blinded. Thermal image analysis was performed offline by an assessor not involved in data collection. Raw-data preprocessing/curation ([name]) and statistical analyses ([name]) were conducted by team members who did not take part in the experimental procedures and were blinded to group allocation.

13. Statistical Analysis Plan (SAP)

- **Descriptives:** values as mean \pm SD; Table 1 additionally reports min–max where shown.
- **Normality:** Shapiro–Wilk test.
- **Between-group comparisons at prespecified time points:** Student’s t test (normal) or Mann–Whitney U test (non-normal).
- **Within-group pre–post comparisons:** paired Student’s t test (normal) or Wilcoxon signed-rank test (non-normal).
- **Repeated measures:** two-way repeated-measures ANOVA for Tsk (group \times stage; and IRT vs RT within groups), with Bonferroni-adjusted post hoc tests. Effect size: partial η^2 for RM-ANOVA.
- **Significance:** $\alpha = 0.05$; tests two-sided.
- **Analysis set / missing data:** all randomised participants analysed; no imputation (no losses).

14. Data Management and Sharing

De-identified individual participant data (IPD) and the de-identified summary datasets underlying all tables and figures are openly available in Zenodo (DOI: 10.5281/zenodo.17255092) under a CC BY 4.0 license, with no access restrictions or data-use agreement required. The Zenodo record also includes Supplementary File S1 (exact questionnaire wording/anchors) and the full Research Protocol and prespecified Statistical Analysis Plan. De-identified IPD comprise participant-level values for prespecified outcomes and baseline characteristics; direct identifiers, dates, free-text fields, and rare categories were removed or aggregated to minimise re-identification risk. The dataset will be preserved for at least 5 years; enquiries may be directed to the corresponding author.

15. Ethics

Approved by the Bioethics Committee of the Poznań University of Medical Sciences (Resolution No. 360/11). Conducted in accordance with the Declaration of Helsinki. Minimal risk expected.

16. Monitoring and Harms

Adverse events (e.g., excessive pain, skin irritation) monitored throughout; any event recorded with timing, severity, relatedness, and action taken. No interim analyses; trial duration per session ~60–75 minutes.

17. Amendments and Deviations

Any protocol deviations or amendments will be documented with rationale, date, and potential impact on outcomes; none planned at this stage.

18. Dissemination

Results to be submitted to a peer-reviewed journal and presented at scientific meetings. Participants can request a lay summary.

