8.3 Safety/harms

Monitoring for intolerance to cold (excess pain, numbness), skin irritation, or adverse events (e.g., frostbite risk). None anticipated under protocol; record and report any events.

9. Time Schedule of Enrolment, Interventions, and Assessments

Acclimatisation: 15 minutes (supine, hand supported on insulating mat).

Measurements at the following time points:

- I – end of acclimatisation (baseline)
- II – 7th minute of cooling
- III – 15th minute of cooling
- IV – immediately after removing the pack
- V – 5th minute of rewarming
- VI – 10th minute of rewarming
- VII – 15th minute of rewarming
- VIII – 20th minute of rewarming
- IX – 25th minute of rewarming
- X – 30th minute of rewarming

Schedule (✓ = administered):

- IRT (ROI mean Tsk): I, IV–X (eight images total)
- RT (single-site Tsk): continuous at 1-min; aligned to I–X for analysis
- TSS, CS, VAS: I, II, III, IV
- QST (MDT, VDT): I and IV

10. Data Collection Methods

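### MDT and VDT: the natural between-group test of change (IV–I) is valid but inefficient, because the stage-I value is collected and never used as a covariate

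*Combined protocol and SAP*

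**What the plan says.** Section 3 lists as a secondary objective: "To compare immediate post-cooling changes in mechanical detection threshold (MDT) and vibration detection threshold (VDT"). Section 8.2 defines the endpoints as "MDT change (post-cooling minus baseline; IV–I") and "VDT change (IV–I"). The schedule in section 9 collects both measures before and after the pack: "QST (MDT, VDT): I and IV".

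Section 13 then lists three kinds of test:

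- "Between-group comparisons at prespecified time points", by Student's t or Mann–Whitney U, with no outcome named;
- within-arm pre–post tests: "paired Student’s t test (normal) or Wilcoxon signed-rank test (non-normal");
- "two-way repeated-measures ANOVA for Tsk", which carries the group × stage term but covers skin temperature only.

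No ANCOVA, regression or other baseline-adjusted model appears. Section 10.3 describes the MDT instrument on two scales, "Semmes–Weinstein monofilaments (1.65–6.65; 0.008–300 g"), and does not say which is analysed.

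Section 11 bases the sample size on an independent-samples t test with d = 0.80, asks for 26 per group, and reports 20 and 19 achieved, with power of about 0.68. It labels the findings exploratory.

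**The concern.** The question is between arms and concerns change. Stage I enters the listed analyses only through subtraction, through pairing within an arm, or as a level of stage in the skin-temperature ANOVA. It is never a covariate. Subtracting the baseline fixes its coefficient at 1, whatever the true relation between stages I and IV. Unless the two are very highly correlated, this adds baseline noise that ANCOVA would avoid.

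What is at stake is precision on two key secondary endpoints, in a trial that reached 39 of its 52 planned participants. A smaller part is missing detail: section 13 does not say outright that the between-group line applies to IV–I, and the MDT scale is open. The scale matters for any difference or parametric model, because a difference in grams and a difference in filament number weight participants differently.

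**Working it through.** **Inputs from the documents.** n = 20 and 19, d = 0.80, two-sided α = 0.05 (sections 11 and 13). No losses (section 11).

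**Assumptions.** Normal outcomes and equal SDs at stages I and IV. The correlation r between stages I and IV is not given, so it is varied. The unit of d is not given, so two are shown.

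**1. The plan's own figures.** For a two-sample t test the noncentrality is d × √(n₁n₂/(n₁+n₂)). With 26 per group, power is 0.807 (0.791 with 25), so 26 reproduces. With 20 vs 19 it is 0.80 × √(380/39) = 0.80 × 3.121 = 2.497 on 37 df, giving power 0.682. The stated 0.68 reproduces.

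**2. Three between-arm tests of the same effect, 0.80 in stage-IV SD units.** Variances relative to a stage-IV-only test are:

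- change score: 2(1−r), so the effective d is 0.80/√(2(1−r));
- ANCOVA: 1−r², so the effective d is 0.80/√(1−r²), on 36 df, with noncentrality multiplied by √(35/36) to allow approximately for chance baseline imbalance;
- ANCOVA over change: (1−r²)/(2(1−r)) = (1+r)/2.

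| r | stage-IV t | change t | ANCOVA | variance ratio (1+r)/2 |
|---|---|---|---|---|
| 0 | 0.68 | 0.41 | 0.67 | 0.50 |
| 0.3 | 0.68 | 0.54 | 0.71 | 0.65 |
| 0.5 | 0.68 | 0.68 | 0.79 | 0.75 |
| 0.7 | 0.68 | 0.88 | 0.92 | 0.85 |

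Simulation of ANCOVA (200,000 trials per r) gives 0.669, 0.710, 0.787 and 0.918, with type I error 0.050–0.051. Against the change test, the gain is about 26, 17, 11 and 4 points. Against a stage-IV-only test, ANCOVA loses about 1 point at r = 0 (0.669 vs 0.682) and gains little at r = 0.2 (0.688 vs 0.682).

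**3. The same with 0.80 in change-score SD units.** The stage-IV effect is then 0.80 × √(2(1−r)), and the effective d for ANCOVA is 0.80 × √(2(1−r))/√(1−r²) = 0.80 × √(2/(1+r)), i.e. 1.131, 0.992, 0.924 and 0.868 at r = 0, 0.3, 0.5 and 0.7. The change test has 0.68 at every r. ANCOVA, by the formula in step 2, has 0.92, 0.84, 0.79 and 0.74. The gain shrinks from about 24 points to about 6 as r rises but does not change sign.

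**4. Bounded and discrete scales.** The documents give no distributions, so these simulations rest on assumed ones, at r = 0.5 with an effect of 0.80 SD of the latent scale. For VDT capped at 8, with 20%, 37% or 57% of participants at the ceiling at baseline, Mann–Whitney on change has power 0.66, 0.65 and 0.60; ANCOVA on ranks pooled over both stages has 0.75, 0.73 and 0.68. For MDT on 20 equal filament steps the figures are 0.63 and 0.74. Type I error of the rank ANCOVA is 0.050–0.053. The advantage survives departures of this kind.

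**5. MDT scale.** By section 10.3, 5.00 filament units (6.65 − 1.65) span a force ratio of 300/0.008 = 37,500, or 4.57 on the log₁₀ scale. Filament number is therefore roughly a log-force scale, whereas grams would let the few highest thresholds dominate a mean difference.

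**The case against.** The strongest reply is that nothing here is wrong. Section 8.2 defines the endpoint as IV–I and section 3 speaks of changes, while outcomes tied to specific stages are set out for skin temperature and the subjective scales. Read together, the documents point to a t or Mann–Whitney test on IV–I. Randomisation makes that test valid, and what remains is a preference for efficiency whose size rests on an r the documents do not give. All of that stands, and it is why the point is minor.

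Two stronger readings are tempting and are not supported.

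- A reader might infer that the analyst is free to choose between a stage-IV test and a change test. Under the assumptions of step 2, those two disagree on significance in 30–31% of simulated trials at r = 0.3–0.7, and taking whichever is significant would give a type I error of 8.9–9.3%. But a stage-IV test would not address the endpoint as defined, and no section plans to pick between results.
- A reader might infer that the within-arm tests will stand in for the group comparison. Where both arms share a true standardised change of 0.5, ice alone would be significant in 25.9% of trials. No section says they will be used that way.

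It can also be said that enrolment is complete and the participant data are already posted, so a new lead model adds flexibility. This is a fair caution. It is met by dating the change, calling it post hoc and showing the unadjusted result, not by leaving the baseline unused.

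**Conclusion.** The concern holds as a matter of efficiency. The natural reading of section 13 gives a valid unadjusted test of MDT and VDT change that leaves the collected baseline unused as a covariate. At r = 0.5, ANCOVA raises power from 0.68 to 0.79 whichever unit 0.80 is taken in. Over r = 0 to 0.7 the gain over the change test runs from about 26 down to 4 points in stage-IV SD units, and from about 24 down to 6 in change-score SD units.

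That ANCOVA is the more powerful of the two is secure across the range shown. The size of the gain is not, because r, the SDs and the unit of d are all assumed. The unstated link between the test line and IV–I, and the open MDT scale, are missing details and do not by themselves put a result at risk of bias. The primary endpoint and the sample-size calculation are untouched. Severity: minor.

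**What to change.** Add to section 13:

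> MDT and VDT: ANCOVA of the stage-IV value on group with the stage-I value as covariate; adjusted ice-minus-control difference with 95% CI. MDT is analysed as filament number (log-force scale). If residuals are clearly non-normal, judged by the Shapiro–Wilk test already named in this section, the p-value comes from ANCOVA on ranks pooled over both stages. Within-arm paired tests are descriptive only.

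Record this under section 17 as a dated post hoc amendment, and report the unadjusted t or Mann–Whitney result on IV–I beside it.

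The cost is a few lines of text, one amendment entry and two models on data already held. The downsides are a post hoc change to secondary analyses in an exploratory trial and, if r is near zero, about 1 point of power lost against a stage-IV-only test.

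### Section 13 compares the arms without baseline adjustment; adding the stage-I value as covariate is a cheap gain in precision whose size depends on a correlation the documents do not give

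*Combined protocol and SAP*

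**What the plan says.** Section 13 gives the between-arm comparison as "Student’s t test (normal) or Mann–Whitney U test (non-normal", applied at prespecified time points. Within arms it gives "paired Student’s t test (normal) or Wilcoxon signed-rank test (non-normal". The only model is a "two-way repeated-measures ANOVA for Tsk", by group and stage, with Bonferroni post hoc tests. No covariate or baseline adjustment appears in any section.

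Baseline values exist for the measures concerned. The schedule in section 9 lists "IRT (ROI mean Tsk): I, IV–X (eight images total" and "QST (MDT, VDT): I and IV", and stage I is the end of acclimatisation. Section 12.2 says "Group assignments were concealed until completion of baseline assessments", so the stage-I values are pre-treatment covariates that knowledge of the allocation could not have influenced. Section 12.1 describes simple randomisation with "no blocking or stratification; superiority framework".

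The primary endpoint (section 8.1) is the lowest IRT Tsk over stages IV to X, a post-treatment value with no baseline term. Section 8.2 defines the MDT and VDT endpoints as stage IV minus stage I. Section 11 bases the sample size on an unadjusted t test at d = 0.80, reports 20 and 19 participants against 26 per group planned, gives power of about 0.68, and calls the findings exploratory.

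**The concern.** A baseline measurement of the same quantity is often the best available predictor of the post-treatment value, and here it has already been collected. An unadjusted test on the post value leaves the variance explained by baseline in the error term. A plain change score subtracts the whole baseline value whatever its correlation with the outcome, so it adds noise when that correlation is low. ANCOVA estimates how much of the baseline to subtract.

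Two features make this worth raising. The trial stopped at three quarters of its planned size (39/52 = 0.75). And with simple randomisation of 39 people, the arms are balanced at stage I only in expectation. At stake is the width of the intervals and the chance of detecting a difference of the size planned for.

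**Working it through.** **Inputs.** From the documents: n = 20 and 19, d = 0.80 (section 11, not tied to a named endpoint), two-sided alpha 0.05 (section 13), no losses (section 11). Assumed: the correlation rho between the stage-I and post-treatment values, and the ratio of the arms' SDs. The documents give neither, so ranges are shown.

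**1. The plan's own figures.** By the noncentral t distribution, 26 per group gives power 0.807 and 25 gives 0.791, so 26 is the required number. At 20 vs 19, sqrt(1/20 + 1/19) = 0.320, the noncentrality is 0.80/0.320 = 2.50 on 37 df, and power is 0.682. Both stated figures reproduce.

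**2. Three analyses, equal SDs and slopes.** With d on the post-value SD, the effective effect sizes are:

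- post value: d, 37 df
- change: d / sqrt(2(1 − rho)), 37 df
- ANCOVA: d / sqrt((1 − rho²) × [1 + 1/(N − 4)]), 36 df. At N = 39 the bracket is 1 + 1/35 = 1.029, the price of estimating the slope.

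For example, at rho = 0.5 the ANCOVA variance factor is 0.75 × 1.029 = 0.771.

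| rho | post value | change | ANCOVA |
|---|---|---|---|
| 0 | 0.682 | 0.405 | 0.669 |
| 0.2 | 0.682 | 0.485 | 0.686 |
| 0.3 | 0.682 | 0.538 | 0.709 |
| 0.5 | 0.682 | 0.682 | 0.790 |
| 0.7 | 0.682 | 0.881 | 0.918 |

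Simulation agrees to within about 0.01, with ANCOVA type I error 0.048–0.051. Simulated CI width for ANCOVA relative to the unadjusted test on the post value is 1.015, 0.994, 0.968, 0.879 and 0.726 down the rows.

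Break-even against the post value: (1 − rho²) × 1.029 = 1, so rho is about 0.17. Against change: 1.029 × (1 + rho)/2 = 1, so rho is about 0.94. The gain over change is larger than the gain over the post value only when rho is below 0.5.

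**3. Unequal arms.** Here d is on the root-mean-square SD, control SD equals baseline SD, and power is simulated.

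| ice SD / control SD | rho ice, control | post value | change | ANCOVA |
|---|---|---|---|---|
| 1 | 0.2, 0.9 | 0.68 | 0.72 | 0.82 |
| 2 | 0.2, 0.9 | 0.67 | 0.73 | 0.74 |
| 2 | 0.5, 0.5 | 0.67 | 0.77 | 0.77 |
| 2 | 0.7, 0.7 | 0.67 | 0.90 | 0.89 |
| 2 | 0.5, 0.9 | 0.67 | 0.85 | 0.84 |
| 3 | 0.2, 0.9 | 0.68 | 0.72 | 0.71 |

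At twice the control SD the advantage over change is already nil or slightly negative in three of the four cells. ANCOVA remains ahead of the post-value test in every cell.

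**4. A VDT-like scale.** Steps of one third, capped at 8, with 37% at the ceiling (assumed). Power at rho 0, 0.5 and 0.7 is 0.40, 0.64 and 0.83 for Mann–Whitney on change, 0.63, 0.74 and 0.86 for linear ANCOVA, and 0.64, 0.73 and 0.85 for rank ANCOVA. The ceiling does not overturn the pattern, and type I error stays at 0.045–0.053 for both ANCOVAs.

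**5. Chance imbalance.** The SE of the stage-I mean difference is 0.320 SD, so a gap of at least 0.5 SD arises in about 12% of such trials. At rho = 0.5 that gap moves the post-value difference by 0.5 × 0.5 = +0.25 SD and the change difference by (0.5 − 1) × 0.5 = −0.25 SD.

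**The case against.** The strongest reply is that nothing here is wrong. The unadjusted tests are valid, section 11 already calls the findings exploratory, the data are already deposited (section 14), and all that remains is a post hoc analysis. That stands, and it sets the weight of the point.

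Several stronger readings are tempting but not supported:

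- *The results are biased, or the design fails to balance baseline.* Randomisation balances stage-I values in expectation. Healthy male students, a controlled room, pre-test restrictions and acclimatisation plausibly narrow the spread as well. Chance imbalance costs precision; it is not a bias of the design.
- *Baseline is ignored altogether.* The group-by-stage ANOVA may include stage-I Tsk as a level. It is not a covariate there, however, and that model does not test the minimum over IV to X.
- *MDT and VDT were tested on change, so a large gain is assured.* Sections 3 and 8.2 imply that test, but section 13 speaks only of time points and never states it. If stage IV was compared directly, the gain at low correlations is about nil.
- *ANCOVA always beats the change score.* Only under near-equal SDs. Ice against a pack at limb temperature makes unequal spread a real possibility.
- *The primary endpoint is underpowered.* The d of 0.80 belongs to no named endpoint, and no expected Tsk difference is given. At a true d of 1.0, 1.2 or 1.5, unadjusted power is already 0.86, 0.95 or 0.995.

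The risk of choosing a covariate to suit the result is limited by the statement in section 12.3 that the analysts "did not take part in the experimental procedures and were blinded to group allocation", and by the covariate being the same measure at stage I.

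**Conclusion.** The point holds as a cheap improvement, not as the correction of an error. Against a test on the post value, which is the natural reading for minimum Tsk, ANCOVA gains about 0.11 in power at a correlation of 0.5 and 0.24 at 0.7, and little or nothing at about 0.2 or less. Against a change score, the gain under equal SDs runs from about 0.26 at zero correlation to 0.04 at 0.7. It can disappear or turn slightly negative with the ice SD about twice control. These figures rest on d = 0.80, normal outcomes and assumed correlations and SD ratios. The documents do not establish which row of the tables applies to which endpoint.

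**What to change.** Add to section 13 a baseline-adjusted between-arm difference with 95% CI from ANCOVA, with the stage-I value of the same measure as the covariate:

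- minimum Tsk, adjusted for stage-I IRT Tsk;
- MDT at stage IV, on one named scale (log force or filament number);
- VDT at stage IV by the linear model, with a rank-based ANCOVA named as secondary to it, because the scale is bounded.

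State which between-group test was actually run for MDT and VDT: on stage IV, or on stage IV minus stage I. Because the data are already collected, record the change under section 17 with reason and date, label the adjusted analyses post hoc, and report them beside the original unadjusted tests rather than in their place.

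The cost is one degree of freedom per model, a few lines of text and a re-run on existing data. If the correlation is near zero, about one point of power is lost against the post-value test (0.67 vs 0.68).
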